11.5.2 Secondary Efficacy Analysis

The analysis of change from Baseline in awake objective cough frequency at Weeks 2 and 4 will be conducted as part of the analysis model for the primary endpoint. The analysis of change from Baseline in both 24 hour and night-time (non-waking time) objective cough frequency will be analyzed in the same way as for the primary endpoint. The other secondary endpoints will be also be analyzed using the MMRM except for the global rating of change in cough frequency and in severity. These shall be summarized as categorical endpoints (“worse”, “about the same” and “better”) and analyzed using Mantel-Haenszel methodology. The 7-point scale for degree of change (if they indicate a change) will also be summarized.

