Relevant Screening and Baseline data (i.e. data collected prior to the treatment administration) and demographic characteristics will be summarized descriptively for each treatment group. Efficacy and safety endpoints will be summarized by descriptive statistics for each treatment group and for each time point.

All statistical hypothesis tests and confidence intervals will be two sided, using a type I error rate of 0.05. No adjustment for multiple comparisons will be used for this study.

The primary analysis of log transformed awake objective cough frequency will be conducted via a mixed model for repeated measures (MMRM) with the model including terms for region, baseline log-transformed awake objective cough frequency, treatment group, week, week*region, week*baseline and week*treatment interactions. Subject will be included as a random effect. Dose response analyses will be conducted. The other secondary endpoints will be analyzed using a MMRM except for the global rating of change in cough frequency and in severity which will be analyzed using Mantel-Haenszel methodology.

The safety and tolerability profile will be assessed versus Baseline conditions and differences between treatment groups and descriptive statistics will be produced, where applicable.

Plasma concentrations of orvepitant will be summarized descriptively; possible exposure-response relationships will be explored.

PLANNED DATE OF FIRST SUBJECT ENROLLED

01-Apr-2017

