The primary endpoint will be change from Baseline to Week 12 in awake objective cough frequency measured with an automated cough monitor (ACM), [REDACTED]. The use of acoustic cough counting to objectively assess cough frequency is recognized as a valid and increasingly preferred tool for primary endpoint determination in cough clinical studies (Spinou & Birring, 2014; Boulet et al., 2015).

Secondary endpoint measures to be utilized that will aim to further characterize the CRC treatment outcomes will include awake objective cough frequency changes at other clinic visits and the validated Quality-of-Life assessment tool the Leicester Cough Questionnaire (LCQ) (Birring et al., 2003; Spinou & Birring, 2014; Boulet et al., 2015). Other patient-reported outcome instruments that will be deployed are the Cough Severity visual analogue scale (VAS), a simple to use tool that is widely utilized in cough clinical studies (Morice et al., 2007), the Urge-to-Cough VAS (Spinou & Birring, 2014) and the Global Rating of Change for Cough Frequency and Severity. Safety and tolerability will be evaluated through conventional assessments used in the evaluation of investigational medicinal products (IMP).

The pharmacokinetic (PK) profile of orvepitant in the target population will be characterized through collection of sparse samples from all subjects. Sparse sampling is a well-established method of collecting PK data that avoids the need for multiple blood draws and extended clinic visits.

6. **STUDY OBJECTIVES AND PURPOSE**

6.1 **Primary objectives**

- To evaluate the efficacy of once daily doses of 10 mg, 20 mg, and 30 mg orvepitant versus placebo in reducing awake objective cough frequency.

6.2 **Secondary objectives**

- To evaluate the efficacy of once daily dosing of 10 mg, 20 mg, and 30 mg orvepitant versus placebo in:
 - Reducing 24-hour objective cough frequency
 - Reducing night-time (non-waking time) objective cough frequency
 - Reducing subject assessed cough severity and Urge-to-Cough
 - Improving Quality-of-Life and subject perception of change
- To evaluate the dose-response relationship of 10 mg, 20 mg, and 30 mg orvepitant

- To assess the safety and tolerability of 10 mg, 20 mg, and 30 mg orvepitant versus placebo over 12 weeks dosing

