8.2 Secondary efficacy endpoints

The secondary efficacy endpoints include:

Objective awake cough frequency changes:

- Change in awake objective cough frequency at Weeks 2, and 4 compared to Baseline
- Change in 24-hour objective cough frequency at Weeks 2, 4, and 12 compared to Baseline
- Change in night-time (non-waking time) objective cough frequency at Weeks 2, 4 and 12 compared to Baseline

The validated Quality-of-Life assessment tool the LCQ.

- Change in the LCQ score (total and three domain scores) at Weeks 2, 4, 8, and 12 compared to Baseline

The Cough Severity VAS, the Urge-to-Cough VAS and the Global Rating of Change for Cough Frequency and Severity.

- Change in the Cough Severity VAS at Weeks 2, 4, 8, and 12 compared to Baseline
- Change in the Urge-to-Cough VAS at Weeks 2, 4, 8, and 12 compared to Baseline
- Global Rating of Change in Cough Frequency and Severity at Weeks 2, 4, 8, and 12

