9.3 Allocation to Treatment

The study will be conducted in a double-blind manner, with the subjects, Investigators and Sponsor all blinded to the treatment allocated. Both orvepitant (10 mg, 20 mg, and 30 mg) and placebo will be presented as white tablets, identical in size and shape.

Following the Screening period and confirmation of eligibility, subjects in each cohort will be randomized in a 1:1:1:1 ratio to receive either orvepitant 10 mg/day, 20 mg/day 30 mg/day or placebo. Randomization will be stratified by region, namely North America and Europe.

The IMP each subject will receive will be allocated by an IWRS tool provided by [REDACTED] on behalf of the Sponsor.

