10.2.5 Global Rating of Change Questionnaire for Cough Frequency and Severity

In the Global Rating of Change Scale subjects will indicate if there has been a change in their symptoms (cough frequency and, separately, cough severity) since starting the IMP. They will respond with “worse”, “about the same” or “better”. If they indicate a change (either “worse” or “better”) they will then further indicate on a 7-point scale the degree of change ranging from 1 (almost the same, hardly any change) to 7 (a very great deal changed).

Subjects will document their Global Rating of Change in Cough Frequency and Cough Severity at Weeks 2, 4, 8, and 12.

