11.3 Data Analysis

More details of the proposed statistical analysis will be documented in the statistical analysis plan (SAP), which will be written following finalization of the protocol and finalized prior to the breaking of the blind.

For continuous data and for ordered categorical data, if appropriate, the number of non-missing observations, mean, standard deviation, median, first and third quartiles, minimum and maximum will be calculated. For ordered categorical data and nominal data, absolute counts and relative frequencies (in %) will be calculated.

All statistical hypothesis tests and confidence intervals will be two sided, using a type I error rate of 0.05. No adjustment for multiple comparisons will be used for this study.

Raw data will be listed.

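### Is it a flaw that the Global Rating of Change is tested only as worse, about the same or better, while its 1–7 degree is merely summarised?

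*Protocol*

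**What the plan says.** Section 10.2.5 describes a two-step instrument, completed separately for cough frequency and cough severity. The subject first gives a direction (worse, about the same, better). Anyone reporting a change then grades it from "1 (almost the same, hardly any change) to 7 (a very great deal changed").

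Section 8.2 lists the secondary endpoint as "Global Rating of Change in Cough Frequency and Severity at Weeks 2, 4, 8, and 12". It does not make the degree an endpoint of its own. The related secondary objective in Section 6.2 is "Improving Quality-of-Life and subject perception of change".

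Section 11.5.2 takes the three directions as the categorical endpoint, "and analyzed using Mantel-Haenszel methodology. The 7-point scale for degree of change (if they indicate a change) will also be summarized". The synopsis names the same method: the other secondary endpoints go to MMRM "except for the global rating of change in cough frequency and in severity which will be analyzed using Mantel-Haenszel methodology". Section 11.3 adds "No adjustment for multiple comparisons will be used for this study" and leaves further analysis detail to the SAP, to be finalised before the blind is broken.

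**The concern.** Direction and degree together form an ordered scale of 15 levels, from −7 through 0 (about the same) to +7. The planned test sees three of them. A subject who is better by the smallest degree counts exactly like one who is better by the largest. The tested boundary thus separates two nearly identical answers, no change and hardly any change, while the much wider contrast within better goes untested.

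If many subjects in every arm answer better, direction alone would separate the doses poorly and most of the information would lie in the degree. At stake would be power on two secondary endpoints that serve a stated objective, in a study meant to identify a dose for Phase 3.

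**Working it through.** **The plan's own figure.** No power is stated for the Global Rating of Change. The only stated power is for the primary endpoint (Section 11.1): 65 per arm, SD 0.285 on the log10 scale, reductions of 10% and 35%, two-sided 5%. The difference is log10(0.90) − log10(0.65) = 0.1413. Power comes out at 80.7% (normal approximation) or 80.1% (t test), which reproduces the stated 80%. The standardised effect is 0.1413 / 0.285 = 0.496 SD. It is borrowed below only as a reference size; nothing in the protocol ties it to the global rating.

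**What follows without assumptions.** The scale has 7 + 1 + 7 = 15 levels. If treatment moves subjects only within better, the three category proportions are equal in the two arms. The three-category statistic then has its null distribution and rejects at its level. This holds for any collapsed scale.

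**What needs assumptions.** The protocol gives no response rates for this endpoint, so all of these are assumed: 65 per arm, two-sided 5%, five placebo mixes, and two sets of degree shares (equal, or weighted to the low degrees). Each case used 20,000 simulated trials and a rank test with tie correction in a single stratum. The first two comparisons below are at 0.496 SD.

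| Placebo worse/same/better (%) | Whole scale shifts: 3 v 15 levels | Only direction changes: 3 v 15 levels | Only degree within better changes: 15 levels |
|---|---|---|---|
| 25/50/25 | 70% v 75% | 70% v 68% | 5–7% |
| 15/45/40 | 67% v 75% | 67% v 61% | 9–14% |
| 15/35/50 | 64% v 76% | 65% v 54% | 14–27% |
| 15/25/60 | 60% v 77% | 60% v 44% | 24–48% |
| 10/20/70 | 53% v 77% | 53% v 32% | 40–73% |

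In the last column the mean degree among those better rises from 3.1 to 4.2 or 4.9, and the three-category test stays at about 5%. Over shifts of 0.3 to 0.6 SD, the 15-level test gains 2.9 to 24.3 points under a whole-scale shift and loses 0.9 to 27.1 points if only direction changes.

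**A second set of assumptions.** Here the test is stratified by region, with 10% worse and 40–60% better on placebo and a mean degree of 3.

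- Shift only within better, by 1 to 3 points: three categories about 4–6%, signed scale 12–93%.
- Better rises from 50% to 65% and degree by 1 point: 36–39% v 81–86%.
- Better rises from 50% to 65% with degree unchanged: 36–40% v 31–34%.

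The direction of each result is the same; the size depends entirely on the assumed pattern.

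**Validity and cost.** Under no effect, each test rejects 4.8–5.2% of the time in the first set and 4.5–4.8% in the second, so the planned test holds its level. A second test would add 2 ratings × 3 doses × 4 visits = 24 unadjusted tests. The chance that at least one of the two tests is significant would be 5.7% to 7.9% per comparison instead of 5%.

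**What the plan does with the degree.** Section 11.5.2 has it summarised. Section 11.3 provides counts and percentages for ordered categorical data and, where appropriate, mean, SD, median, quartiles and range. A shift within better would be visible by arm; what is lacking is a p-value. The LCQ and both VAS, which are graded subject-reported scales, are analysed by MMRM at the same four visits.

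**The case for a change.** The best case for the concern is that Section 11.5.2 does more than leave a detail open. It fixes which form of the rating is tested and gives the degree a descriptive role. The blindness of the three-category test to a shift within better is a certainty, not a simulation result. The ACCP guideline in Appendix A warns of strong placebo effects on cough, so a high share of better on placebo is plausible, and that is where the loss under a whole-scale shift is largest (53% v 77% at 10/20/70). The remedy would be a sentence or two in the same Mantel-Haenszel family, stratified by the randomisation factor ("Randomization will be stratified by region, namely North America and Europe"), with no new data.

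The description of the text and of the blind spot stands. The step from there to a flaw does not. A high share of better also gives the full-scale test its worst result when only direction moves (53% v 32% at the same mix), and the protocol gives no reason to expect one pattern over the other. A comparison of direction is a legitimate and easily read choice. Nothing in Section 11.5.2 rules out a supportive analysis of the degree, and the general reference to Mantel-Haenszel methods leaves scores and strata to be specified. That is ordinary SAP content.

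**Conclusion.** The concern does not hold. The protocol states nothing wrongly here and does not contradict itself. The planned test is valid, and the objective on perceived change is tested for both ratings through direction. The degree is reported, and graded subject-reported outcomes are tested elsewhere.

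What remains is a preference for an additional supportive test. Its benefit is a trade-off: about 3 to 24 points gained if the whole scale shifts, about 1 to 27 points lost if direction alone changes, and 5% to 73% power against about 5% if only the degree changes. All these figures rest on assumed response rates, on 65 per arm and on a shift size partly borrowed from cough frequency. Only the 5% rejection rate of the three-category test against a shift confined to better needs no such assumption.

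No sample size, decision rule or primary inference depends on this endpoint. In an exploratory Phase 2 study without multiplicity control, 24 further supportive tests would change no stated conclusion. The SAP was not available for this review and may already include such an analysis.

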11.6 Statistical Methods for Safety Parameters

Safety data will be summarised descriptively for each treatment group. No formal inferential tests will be performed on safety data.

The number of treatment emergent AEs (TEAEs), and subjects with TEAEs, will be compared between groups. TEAEs are defined as AEs that first occurred or worsened in severity after the first dose of IMP.

TEAEs will be summarised for all causality AEs and for treatment-related AEs (those with related relationship to IMP and missing). TEAEs will be summarised by MeDRA body system and preferred term. TEAEs will also be reported by severity.

Any deaths, SAEs and AEs leading to discontinuation of IMP administration will also be summarised by treatment group.

SAEs will be presented in a similar way to AEs.

Vital signs will be summarised for each treatment group by visit. Summary statistics will be presented for absolute values and the change from Baseline.

ECGs will be assessed by the Investigator for abnormal findings. These will be categorised and summarised as normal, abnormal-not clinically significant or abnormal-clinically significant. ECG intervals will be recorded and summarised as absolute values and changes from Baseline.

Clinical laboratory data for individual subjects will be listed and any out of range values will be highlighted. Laboratory data will be summarised for each treatment group by visit. Summary statistics will be presented for absolute values and change from Baseline, as well as an analysis of shifts from Baseline.

Extent of exposure and compliance will be evaluated.

11.7 Pharmacokinetics Analysis

The plasma orvepitant concentrations will be analyzed using a population pharmacokinetic (Pop PK) approach by nonlinear mixed effects modeling (NONMEM®). The Pop PK model will be used to evaluate the relationship between orvepitant exposure and clinical endpoints. The details of the analysis will be described in a Pop PK Data Analysis Plan (DAP).

11.8 Missing Data

Summary statistics will be based primarily on non-missing values. For hypothesis tests, estimates and confidence intervals, missing values for continuous efficacy endpoints analyzed via likelihood methods (e.g. repeated measures mixed models) will not be directly imputed as they are handled within the analysis itself, under the assumption that the model specification is correct and that the data is missing at random. Sensitivity analyses may be conducted to check the robustness of the analysis results under alternative assumptions with regards to missing data. Further details on the handling of missing values, including rules applied to incomplete questionnaires and any planned sensitivity analyses will be defined in the SAP.

12. END OF THE STUDY

The end of the study will be defined as the last subject's last visit.

13. ETHICS COMMITTEE REVIEW/INFORMED CONSENT

13.1 Institutional Review Board (IRB) / Independent Ethics Committee (IEC) and Relevant Authorities

The final study protocol, the subject information and consent form and any other subject facing materials (e.g. questionnaires, advertisements) will be approved by an appropriately constituted IRB/IEC. Approval will be received in writing before initiation of the study.

Clinical Study Authorization will be obtained prior to initiation of the study from the relevant Regulatory Authority.

13.2 Ethical Conduct of the Study

The study will be performed in accordance with the local regulations, the principals of Good Clinical Practice (GCP) as described by the International Council for Harmonization (ICH), and the ethical principles that have their origins in the Declaration of Helsinki.

13.3 Informed Consent

For each study subject, written informed consent will be obtained prior to any protocol-related activities. As part of this procedure, the principal investigator or one of his/her associates will explain orally and in writing the nature, duration, purpose of the study, and the action of the study drug in such a manner that the subject is aware of the potential risks, inconveniences, or adverse

effects that may occur. They will be informed that their medical records may be reviewed by appropriately qualified monitors of the Sponsor or Sponsor Representative, and by auditors or regulatory authorities to ensure the accuracy of the details recorded as part of the study. They will be informed that they may withdraw from the study at any time without prejudice to further treatment. They will receive all information that is required by local regulations and ICH guidelines.

14. STUDY AND DATA MANAGEMENT

14.1 Protocol Amendments

Once approved by the applicable Regulatory Authorities and IRBs/IECs, the protocol must not be amended without approval by NeRRe. Unless an amendment is required to be implemented urgently in the interests of safety, or is deemed administrative by NeRRe, any amendments to the protocol must be authorized by the applicable Regulatory Authorities and IRB/IEC prior to implementation.

14.2 Monitoring

In accordance with applicable regulations including GCP and NeRRe or delegated CRO's Standard Operating Procedures (SOP), approved clinical research monitors will contact the site prior to the start of the study to review with the site staff the protocol, study requirements, and their responsibilities to satisfy regulatory, ethical, and NeRRe requirements. When reviewing data collection procedures, the discussion will also include identification, agreement and documentation of data items for which the eCRF will serve as the source document. A list of what is to be classed as 'source documentation' will be documented in the Study Monitoring Manual.

NeRRe will monitor the study and sites to verify:

- Data are authentic, accurate and complete
- Safety and right of the subjects are being protected
- IMP accountability
- SAE reporting
- Study is conducted in accordance with the currently approved protocol and any other study agreements, GCP and all applicable regulatory requirements

The investigator[s]/institution[s] will permit study-related monitoring, providing direct access to source data/documents.

14.3 Quality Assurance

To ensure compliance with GCP and all applicable regulatory requirements, the investigator[s]/institution[s] will permit study-related audits, IRB/IEC review, and regulatory inspection[s], providing direct access to source data/documents.

14.4 Data Recording

14.4.1 Data to be Considered as Source Data

An eCRF will be used to capture subject data into a secure, validated database. Access to enter data in the eCRF will be limited to delegated and trained investigator site staff only. ACM, PK and safety laboratory data will be transferred electronically into the database periodically during the study.

Source data may be defined as information from an original record or certified copy of the original record containing patient information for use in the trial. The information may include, but is not limited, to clinical findings, observations, or other activities necessary for the reconstruction and evaluation of the trial. Source data are contained in source documents (original records or certified copies) (ICH E2A Guideline). Examples of source data include subject identification and randomization identification.

14.5 Confidentiality

The Investigator must assure that the subjects' anonymity will be maintained. On all study documentation, with the exception of the consent form and subject ID logs, subjects will only be identified by their unique identification code and initials and will not be referred to by name.

Study data will be handled with utmost discretion within the context of physician's confidentiality. On the eCRFs and other study specific documents, subjects are not identified by their names, but by a unique subject number. Names of participating subjects and data generated as a result of this study will not be passed on to unauthorized persons.

The Investigator must assure that the subjects are properly anonymized throughout the study. On all study documentation which is supposed to leave the site (i.e., to be transmitted to NeRRe, CRO or third parties), subjects will only be identified by their unique identification code and will not be referred to by name.

NeRRe may transfer some data collected during the study to a different company or regulatory authority outside of the US or EU for the purpose of processing, review, analysis or storage. Whenever the subject's personal data is transferred, it will be kept confidential and secure, and will be used only for the purpose for which it was collected.

Safety analysis samples collected during the study will be analyzed at a central laboratory. Samples will be identified by the subjects' unique identification code. All safety samples will be destroyed after the assays have been completed.

Blood samples for analysis of orvepitant concentrations will be shipped to Aptuit Srl, Italy for analysis. Samples will be identified by the subjects' unique identification code. Following completion of the analysis, all samples will be destroyed.

